#### 8.7.1.6.2 SECONDARY EFFICACY ANALYSES

PFS-1y rate will be analyzed using the same methods as the primary efficacy analysis. PFS censoring rules will follow FDA guidance of 2007, however, removal of baseline lesions after completion of Week 18 without progression is not a trigger for PFS censoring after 18 weeks. (refer to [Section 8.4.7.3](#) for allowed concomitant treatments/procedure in the study).

Overall survival (OS) will be compared between treatment arm and control arm using the stratified logrank test with time to first relapse/refractory disease (early [ $<18$  months] or late [ $\geq 18$  months]) and age ( $<18$  or  $\geq 18$  years) as strata. Median OS with 2-sided 80% and 95% CIs will be calculated using K-M product-limit estimates for each treatment arm, and the K-M estimates of OS will be plotted over time. The Cox regression model will be used to estimate the hazard ratio and its 80% and 95% CIs stratified by time to first relapse/refractory disease (early [ $<18$  months] or late [ $\geq 18$  months]) and age ( $<18$  or  $\geq 18$  years). Kaplan-Meier (K-M) estimates will also be presented for 4, 6, 9 and 12 months with 2-sided 80% and 95% CIs.

Overall PFS will be analyzed similarly to OS. Median PFS and 2-sided 80% and 95% (as exploratory) CIs will be presented, and the K-M estimates of PFS will be plotted over time. The Cox regression model will be used to estimate the hazard ratio and its 80% and 95% CIs stratified by time to first relapse/refractory disease (early [ $<18$  months] or late [ $\geq 18$  months]) and age ( $<18$  or  $\geq 18$  years). K-M estimates will also be presented for 4, 6, 9, and 12 months with 2-sided 80% and 95% CIs.

The ORR will be compared between the test and control groups using either a chi-square test or a Cochran-Mantel-Haenszel test stratified by time to first relapse/refractory disease (early [ $<18$  months] or late [ $\geq 18$  months]) and age ( $<18$  or  $\geq 18$  years), as appropriate. Corresponding odds ratios and their 2-sided 80% and 95% CIs comparing the groups will also be presented. The individual treatment group ORRs will also be calculated along with exact 95% confidence intervals using the Clopper and Pearson method.

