#### 8.7.1.6.1 PRIMARY EFFICACY ANALYSIS

The primary analysis of PFS-4m rate will be based upon data provided by IIR of tumor assessments. PFS-4m rate and their Greenwood standard errors will be evaluated using the K-M estimates from both treatment groups. The statistical significance of the difference in the 2 K-M PFS-4m rates comparing lenvatinib + chemotherapy agent (Test Arm) vs. chemotherapy agent alone (Control Arm) will be tested using a 2-sided 80% CI. This 2-sided

80% CI and a p-value will be constructed using the difference of these 2 K-M PFS-4m rates and the 2 corresponding Greenwood standard errors. Statistical significance of the difference is declared if the CI is entirely above 0. This is equivalent to a test using a 1-sided test at alpha=0.1. The 2-sided 95% CIs will also be provided for descriptive purposes. PFS-4m rate will also be analyzed using a binomial approach as a sensitivity analysis by excluding subjects whose PFS are censored prior to 18 weeks.

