### **8.7.2 Determination of Sample Size**

A binomial-based comparison of 2 proportions using correction for continuity was used for sample size estimation. A total sample size of 72 subjects is estimated to achieve 80% statistical power at 1-sided alpha of 0.1 to detect a difference of 30% based on the assumption that PFS-4m for Arm A (lenvatinib arm) is 55% and for Arm B is 25%. Alpha is the type 1 error probability of declaring lenvatinib arm being effective when the true lenvatinib arm PFS-4m rate is only 25%.

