### **Number of Subjects**

Approximately 72 subjects will be randomised (36 subjects in each arm).

For the primary endpoint (intent-to-treat analysis), at least 32 subjects  $< 18$  years old (at the time of informed consent) will be randomized.

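### PFS-1y inherits the primary Greenwood difference interval, which has no defined standard error if the Arm B Kaplan-Meier estimate reaches 0 by 1 year; the protocol states no rule for that case

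*Protocol*

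**What the plan says.** Section 8.7.1.6.2, and Secondary Analyses in the synopsis, state: "PFS-1y rate will be analyzed using the same methods as the primary efficacy analysis". Section 8.7.1.6.1 defines that method: "80% CI and a p-value will be constructed using the difference of these 2 K-M PFS-4m rates and the 2 corresponding Greenwood standard errors". The decision rule is "Statistical significance of the difference is declared if the CI is entirely above 0", and the text adds: "This is equivalent to a test using a 1-sided test at alpha=0.1". A 95% interval is also given as descriptive.

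The only control rate in the protocol is in section 8.7.2: "PFS-4m for Arm A (lenvatinib arm) is 55% and for Arm B is 25" per cent. The synopsis plans 36 subjects per arm. No 1-year rate, curve shape or dropout rate is stated, and nothing is said about an arm whose estimate is 0 at the time point. Section 8.7.1.6.2 also says that removing baseline lesions after Week 18 without progression does not censor PFS, and it compares the whole PFS curve by stratified logrank test and Cox model.

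**The concern.** A difference interval built on Greenwood standard errors is a large-sample device. At 4 months, with assumed rates of 55% and 25% in 36 subjects per arm, both arms should have enough subjects event-free and enough events. At 1 year the control arm may have very few subjects event-free, or none.

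If the Arm B curve has reached 0, the analyst must either report that no interval exists or set the Arm B standard error to 0, which treats a rate estimated from 36 subjects as known exactly. The protocol chooses neither. In an open-label trial that choice would be made after the control tail is visible. PFS-1y is the first-listed secondary objective and is a between-arm comparison with a significance rule, so its interval will be read.

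**Working it through.** **Inputs.** From the protocol: 36 per arm; PFS-4m of 55% and 25%; one-sided alpha 0.1 (z = 1.2816); the scan schedule (Week 45 is the last nominal scan before 1 year); earlier-study data in section 6.3.1. Curve shapes, censoring levels and 1-year rates are assumptions, shown as ranges.

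**The plan's own figure.** Section 8.7.2 gives 72 subjects for 80% power. The continuity-corrected two-proportion formula at one-sided 0.1 for 25% vs 55% gives 30 per arm (60 in total), and about 87% power at 36 per arm. So 72 is not reproduced from the stated inputs. The gap is conservative and a separate matter; only n = 36 is used below.

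**Why the standard error fails.** Greenwood's variance is S² × Σ d/[n(n − d)]. When the last subject at risk has an event, n = d: the sum divides by zero while S² = 0. Without censoring the formula reduces to S(1 − S)/n, which is 0 at S = 0. Arm B then adds no uncertainty.

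**How often Arm B is at 0.** Without censoring, P = (1 − S)^36, where S is the Arm B rate at 1 year, or at the last scan before it.

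| Assumption | S | P(estimate = 0) |
|---|---|---|
| Constant hazard, 0.25^3 | 1.56% (0.56 of 36 subjects) | 57% |
| Same, events dated at scans: 0.25^(10.35/4), Week 45 = 10.35 months | 2.8% | 36% |
| Same, 25% read as the rate after the Week 12 scan: 0.25^(45/12) | 0.55% | 82% |
| Weibull shape 0.57 | 7.5% | 6% |
| Weibull shape 1.72 | 0.01% | over 99% |
| True 1-year rate 5% | 5% | 16% |
| True 1-year rate 10% | 10% | 2% |

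The Weibull shapes come from k = ln[ln 0.5 / ln S(4)] / ln(median/4). The earlier combination data (67.9% at 4 months, median 11.1 months) give k = 0.57. The single-agent data (32.1%, 3.0 months) give k = 1.72. Arm B at 1 year is then 0.25^(3^k). Simulating constant hazard on the scan schedule with 20-40% censoring by 1 year gives 42-47%. P exceeds one half only if S is below 1.9%.

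**Behaviour with the Arm B standard error set to 0.** Exact enumeration of all outcomes at 36 vs 36, uncensored:

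- Type I error of the 80% rule at common 1-year rates of 1.56%, 2.5%, 5% and 10%: 6.2%, 9.6%, 11.9% and 10.6%, against 10%.
- Coverage against 1.56% in Arm B (the last Arm A rate is 0.55^3):

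| True Arm A rate | 95% CI, plan | 95% CI, hybrid | 80% CI, plan | 80% CI, hybrid |
|---|---|---|---|---|
| 5% | 84% | 99% | 75% | 86% |
| 10% | 87% | 98% | 77% | 83% |
| 16.6% | 93% | 97.5% | 77% | 82% |

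The hybrid takes Wilson limits per arm and combines them by square-and-add. The shortfall belongs to the plain interval at very low counts in general, not only to outcomes with a zero in Arm B.

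**One outcome worked through.** 2/36 vs 0/36: the difference is 5.6% and the standard error √(0.0556 × 0.9444/36) = 3.8%. The 80% interval is 5.6 ± 1.2816 × 3.8, or 0.7% to 10.5%. In the hybrid interval Arm B has a Wilson upper limit of z²/(n + z²) = 1.642/37.642 = 4.4%, and the Wilson lower limit for 2/36 is 2.3%. The lower limit is 5.56 − √(3.22² + 4.36²) = 0.1%. Both declare significance, although the one-sided Fisher p is 0.25.

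**Effect on decisions.** The two 80% rules agree in all 37 × 37 = 1,369 uncensored tables and in about 98-99.5% of censored simulations.

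**The case against.** The strongest reply has four parts.

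- **The zero is not established.** The protocol commits to 25% at 4 months only. The earlier combination data imply a flattening curve; lesion removal after Week 18 does not censor and can leave resected subjects event-free. This stands. A reader might infer that the control curve is likely to be at 0 by 1 year; the documents do not support that, because it needs a constant hazard they never state. Even with it, the scan-schedule figure is 36%.
- **The rule still runs.** With the standard error taken as 0 it returns a decision, with type I error near nominal. This also stands. A reader might infer that the test cannot be applied, or that power collapses from 90% to 34% at 16.6% vs 1.6%. The 34% arises only if an undefined test is counted as not significant, a convention the protocol does not adopt.
- **The remedy changes almost no decision, and the usual effective sample size, S(1 − S)/variance, is itself 0/0 at S = 0.** Both are correct. The gain is computability and coverage, and the remedy must define the sample size at 0.
- **This is SAP detail.** Section 8.7.1 leaves further details to the SAP, which was not available here and may already name a fallback. But the protocol fixes a specific method for PFS-1y, so such a fallback would depart from the stated rule. This part does not remove the point.

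**Conclusion.** The point holds as a limited one about a secondary endpoint. The protocol prescribes for PFS-1y an interval whose standard error is undefined when an arm's estimate is 0, without stating the convention to use. How often this arises depends on an unstated curve: about 36-57% at constant hazard through 25% at 4 months, and 6% to over 99% across shapes suggested by the earlier data. With the standard error set to 0, the significance test behaves tolerably (type I error about 6-12%). The intervals do less well when the arms differ: 84-93% coverage for a nominal 95%, and 75-77% for a nominal 80%. These figures assume 36 per arm and no censoring.

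The documents do not support reading this as a broken test. The primary PFS-4m analysis is untouched, the logrank and Cox comparisons of PFS do not fail when Arm B reaches 0, and no testing hierarchy depends on PFS-1y. The change is worth making because it removes an analyst's choice after the data are seen.

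**What to change.** In section 8.7.1.6.2 and in Secondary Analyses of the synopsis, replace the cross-reference to the primary method, for PFS-1y only, with text to this effect:

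- The difference in Kaplan-Meier PFS-1y rates is reported with a 2-sided 80% hybrid score interval (95% as descriptive): Wilson limits for each arm, combined by square-and-add.
- The effective sample size in each arm is S(1 − S) divided by the Greenwood variance when S is above 0. When S is 0 it is the number randomised to that arm minus those censored before 1 year.
- The criterion stays as it is (80% interval above 0), and PFS-4m is unchanged.

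With the effective sample size so defined, censored simulations gave 97-99.9% coverage for the 95% interval. The cost is a sentence or two of protocol and SAP wording and a few lines of code. The downside is a wider, somewhat conservative interval at very low rates. The change does not make the test stricter: 2 vs 0 event-free subjects would still narrowly count as significant.

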#### 8.7.1.6.3 EXPLORATORY EFFICACY ANALYSES

Median DOR among responders for each arm will be presented along with its corresponding 2-sided 95% CIs. Disease Control Rate (DCR) and CBR will be calculated with exact 95% CIs using the Clopper and Pearson method. The differences of the above rates between 2 groups and corresponding two-sided 95% CIs will be calculated respectively.

### 8.7.1.7 Pharmacokinetic, Pharmacodynamic, and Other Biomarker Analyses

#### 8.7.1.7.1 PHARMACOKINETIC ANALYSES

Lenvatinib concentration versus time data will be tabulated and summarized and graphically presented.

Lenvatinib data from Arm A of the study will be pooled with available data from other studies and subjected to population PK analysis. The PK model will be parameterized in terms of clearance and volume of distribution. Details of the population PK analysis will be provided in a separate analysis plan.

#### 8.7.1.7.2 PHARMACODYNAMIC AND OTHER BIOMARKER ANALYSES

Pharmacodynamic, and other biomarker analyses may be performed and reported separately. Details of these analyses may be described in a separate analysis plan.

Pharmacodynamic serum and archived, fixed tumor tissue biomarkers will be collected from subjects in Arm A only as described in the Schedule of Assessments. Pharmacodynamic serum and tumor biomarkers in this study will be identified as in other lenvatinib clinical studies.

Blood serum samples may be analyzed using global proteomic methods, enzyme-linked immunosorbent assay (ELISA), multiplex bead-based immunoassay, or other assays/methods and new technology in an effort to identify biomarkers.

Archived, fixed tumor tissue will be collected (if available) for assessment of mutations and other genetic alterations or proteins that may be important in the development and progression of cancer as well as for potential use in diagnostic development.

Data obtained from the pharmacodynamic samples will be used for research. The pharmacodynamic samples will not be used to determine or predict risks for diseases that an individual subject does not currently have. Any sample or derivatives (DNA, RNA, and protein) may be stored for up to 15 years to assist in any research scientific questions related to lenvatinib and for potential diagnostic development. If the subject reaches 18 years of age prior to the date of final sample analyses they will be reconsented. No further analyses will be performed on these collected samples from subjects who either do not reconsent after their 18th birthday or cannot be reached for reconsenting and the sample will be destroyed. When the subject reaches the age of 18 years (or 16 years in the UK) while on the study, and becomes competent to give informed consent, his/her consent will be obtained using separate ICFs to continue on the study.

### 8.7.1.8 Safety Analyses

All safety analyses will be performed on the Safety Analysis Set. Safety data, presented by treatment group, will be summarized on an “as treated” basis using descriptive statistics (eg, n, mean, standard deviation, median, minimum, maximum for continuous variables; n [%])

for categorical variables), as appropriate. Safety variables include TEAEs, clinical laboratory parameters, vital signs, 12-lead ECG results, Lansky play scores or Karnofsky performance scores, physical examination, height, closure of proximal tibial plates, and LVEF. Study Day 1 for all safety analyses will be defined as the date of the first dose of study drug.

#### 8.7.1.8.1 EXTENT OF EXPOSURE

The number of cycles/days on treatment, quantity of study drug administered, and the number of subjects requiring dose reductions, treatment interruption, and treatment discontinuation due to adverse events will be summarized.

#### 8.7.1.8.2 ADVERSE EVENTS

The AE verbatim descriptions (investigator terms from the CRF) will be classified into standardized medical terminology using the Medical Dictionary for Regulatory Activities (MedDRA). Adverse events will be coded to the MedDRA (Version 20.1 or higher) lower level term (LLT) closest to the verbatim term. The linked MedDRA preferred term (PT) and primary system organ class (SOC) are also captured in the database.

A TEAE is defined as an AE that emerges during treatment (and within 30 days of the last study treatment), having been absent at pretreatment (Baseline) or

- Re-emerges during treatment, having been present at pretreatment (Baseline) but stopped before treatment,  
or
- Worsens in severity during treatment relative to the pretreatment state, when the AE is continuous.

Only those AEs that are treatment-emergent will be included in summary tables. All AEs, treatment-emergent or otherwise, will be presented in subject data listings.

The TEAEs will be summarized by treatment group. The incidence of TEAEs will be reported as the number (percentage) of subjects with TEAEs by SOC and PT. A subject will be counted only once within an SOC and PT, even if the subject experienced more than 1 TEAE within a specific SOC and PT. The number (percentage) of subjects with TEAEs will also be summarized by highest CTCAE grade.

The number (percentage) of subjects with TEAEs will also be summarized by relationship to study drug (Yes [related] and No [not related]).

The number (percentage) of subjects with treatment-related TEAEs will be summarized by SOC and PT. Treatment-related TEAEs include those events considered by the investigator to be related to study treatment. The number (percentage) of subjects with treatment-related TEAEs will also be summarized by highest CTCAE grade.

Adverse events will be summarized using the Safety Analysis Set. The number of AEs and number and incidence (%) of subjects with AEs will be summarized by treatment group and

overall. To obtain the incidence (%), the number of subjects with at least 1 event and the percentage of subjects with AEs by SOC and by PT will be calculated. Incidence (%) by causal relationship with study drug and by severity (CTCAE v5.0) will also be calculated. For clinically significant events, time of onset, and recovery will be reported.

Adverse events will be summarized for descriptive purposes by age (2 to <6, 6 to <18, and ≥18), and sex.

The number (percentage) of subjects with TEAEs leading to death will be summarized by MedDRA SOC and PT for each treatment group. A subject data listing of all AEs leading to death will be provided. All deaths will also be summarized.

The number (percentage) of subjects with treatment-emergent SAEs will be summarized by MedDRA SOC and PT for each treatment group. A subject data listing of all SAEs will be provided.

The number (percentage) of subjects with TEAEs leading to discontinuation from study drug will be summarized by MedDRA SOC and PT for each treatment group. A subject data listing of all AEs leading to discontinuation from study drug will be provided.

#### 8.7.1.8.3 LABORATORY VALUES

Laboratory results will be summarized using Système International (SI) units, as appropriate. For all quantitative parameters listed in [Section 8.5.1.4.3](#), the actual value and the change from baseline to each postbaseline visit and to the end of treatment (defined as the last on-treatment value) will be summarized by visit and treatment group using descriptive statistics. Qualitative parameters listed in Section 8.5.1.4.3 will be summarized using frequencies (number and percentage of subjects), and changes from baseline to each postbaseline visit and to end of treatment will be reported using shift tables. Percentages will be based on the number of subjects with both nonmissing baseline and relevant postbaseline results.

Laboratory test results will be assigned a low/normal/high (LNH) classification according to whether the value was below (L), within (N), or above (H) the laboratory parameter's reference range. Within-treatment comparisons for each laboratory parameter will be based on shift tables that compare the baseline LNH classification to the LNH classification at each postbaseline visit and at the end of treatment. Similar shift tables will also compare the baseline LNH classification to the LNH classification for the highest and lowest value during the treatment period.

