**Table 1 Criteria for Temporary Discontinuation of Study Drug, Dose Reduction, and Resumption of Treatment**

Dose Modification Guidelines for Lenvatinib Related Toxicity		
Treatment-Related Toxicitya,b	Management	Dose Adjustment
Grade 1 or Tolerable Grade 2		
	Continue treatment	No change
Intolerable Grade 2c,d or Grade 3e		
First occurrence	Interrupt lenvatinib until resolved to Grade 0-1, or tolerable Grade 2	11.2 mg/m  (or 20% reduction of the starting dose) orally QD (one-level reduction)
Second occurrence (same toxicity or new toxicity)	Interrupt lenvatinib until resolved to Grade 0-1, or tolerable Grade 2	9.0 mg/m  (or 20% reduction of the previous dose) orally QD (one-level reduction)
Third occurrence (same toxicity or new toxicity)	Interrupt lenvatinib until resolved to Grade 0-1, or tolerable Grade 2	7.2 mg/m  (or 20% reduction of the previous dose) orally QD (one-level reduction)
Fourth occurrence (same toxicity or new toxicity)	Interrupt lenvatinib	Discuss with sponsor
Grade 4f: Discontinue Study Treatment		

Note: For grading see CTCAE version 5.0. Collect all CTC grades of adverse events, decreasing and increasing grade.

BMI = body mass index, CTCAE = Common Terminology Criteria for Adverse Events

a: An interruption of study treatment for more than 28 days will require sponsor's approval before treatment can be resumed.

b: Initiate optimal medical management for nausea, vomiting, hypertension, hypothyroidism, and/or diarrhea prior to any study treatment interruption or dose reduction.

c: Applicable only to Grade 2 toxicities judged by the subject and/or physician to be intolerable.

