#### **8.4.6 Blinding**

The study will not be blinded.

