#### 8.5.1.4 Safety Assessments

Safety assessments will consist of monitoring and recording all AEs, including all grades per National Cancer Institute (NCI) CTCAE v5.0 (for both increasing and decreasing severity), and serious adverse events (SAEs); regular laboratory evaluation of hematology, blood chemistry, and urine values; periodic measurement of vital signs and 12-lead ECGs; and echocardiograms, Lansky play score or Karnofsky performance status score, physical examinations, and height assessments as detailed in the Schedule of Assessments ([Table 5](#) and [Table 6](#)).

Clinical and laboratory toxicities/symptomatology will be graded according to CTCAE v5.0 ([Cancer Therapy Evaluation Program, 2017](#)).

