#### 8.5.1.4.1 ADVERSE EVENTS

An AE is any untoward medical occurrence in a patient or clinical investigation subject administered an investigational product. An AE does not necessarily have a causal relationship with the medicinal product. For this study, the study drug is lenvatinib.

The criteria for identifying AEs in this study are:

- Any unfavorable and unintended sign (including an abnormal laboratory finding), symptom, or disease temporally associated with the use of an investigational product, whether or not considered related to the investigational product (Note: Every sign or symptom should not be listed as a separate AE if the applicable disease [diagnosis] is being reported as an AE)
- Any new disease or exacerbation of an existing disease. However, worsening of the primary disease should be captured under efficacy assessments as PD.
- Any deterioration in nonprotocol-required measurements of a laboratory value or other clinical test (eg, ECG or x-ray) that results in symptoms, a change in treatment, or discontinuation of study drug
- Recurrence of an intermittent medical condition (eg, headache) not present pretreatment (Baseline)
- An abnormal laboratory test result should be considered an AE if the identified laboratory abnormality leads to any type of intervention, withdrawal of study drug, or withholding of study drug, whether prescribed in the protocol or not

All AEs, regardless of relationship to study drug or procedure, should be recorded beginning from the time the subject signs the study ICF through the last visit and for 30 days after the subject's last dose. Refer to [Section 8.5.4.1](#) for the time period after the end of treatment for SAE collection.

Abnormal laboratory values should not be listed as separate AEs if they are considered to be part of the clinical syndrome that is being reported as an AE. It is the responsibility of the investigator to review all laboratory findings in all subjects and determine if they constitute an AE. Medical and scientific judgment should be exercised in deciding whether an isolated laboratory abnormality should be classified as an AE. Any laboratory abnormality considered to constitute an AE should be reported on the Adverse Event CRF.

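### Minor, cheap improvement: the highest/lowest-value laboratory shift table uses a low/normal/high scale, so it cannot separate a mild fall from a Grade 4 nadir

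*Protocol*

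**What the plan says.** Section 8.7.1.8.3 (Laboratory Values) classes each result as below, within or above the laboratory's reference range. It then says: "Within-treatment comparisons for each laboratory parameter will be based on shift tables that compare the baseline LNH classification" at each postbaseline visit and at end of treatment. For the extremes on treatment it adds: "Similar shift tables will also compare the baseline LNH classification to the LNH classification for the highest and lowest value during the treatment period". The same section summarizes actual values and changes from baseline by visit and treatment group.

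Section 8.5.1.4 (Safety Assessments) uses another scale: "Clinical and laboratory toxicities/symptomatology will be graded according to CTCAE v5.0". Conduct follows that grade:
- Section 8.5.1.4.3 and the hematology footnote of Table 5 call for repeat testing and adverse event assessment at least every 3 days from Grade 3 upward.
- Table 2 calls for neutrophil monitoring at Grade 4 neutropenia.

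In the analysis section, CTCAE grade appears only for adverse events. Section 8.7.1.8.2 summarizes TEAEs by highest grade and by preferred term. On what becomes an adverse event, Section 8.5.1.4.1 says: "Medical and scientific judgment should be exercised in deciding whether an isolated laboratory abnormality should be classified as an AE". Section 8.4.6 states: "The study will not be blinded".

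**The concern.** The lowest-value shift is where a reader would look for the depth of cytopenia on treatment. With a myelosuppressive backbone in both arms, many subjects in either arm can be expected to reach the low class at some point. The informative question is then how low they go, and an LNH scale cannot answer it. Severity is recorded under the protocol's own grading rule and acted on during the trial, but it is dropped from the one laboratory table built on each subject's extreme value.

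At stake is the clarity of the safety comparison named in secondary objective 5 (Section 7.2). Cytopenias were the most common treatment-related Grade 3 or higher events with the same combination in Study 207 (Section 6.3.1).

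**Working it through.** The protocol states no figure to reproduce here. The check sets its rules side by side, with a little arithmetic on one point.

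**1. What the scale merges.** The conduct rules distinguish three bands for a low count: below Grade 3, Grade 3 and Grade 4. LNH has one class for any value under the reference range, so three bands become one. In the shift table the low column is split by baseline class (low, normal, high), but within each row the bands stay merged. If every subject's lowest neutrophil count fell below the lower limit (an assumption for illustration), the low column would total 36 in each arm of 36, whatever the grades.

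**2. Subjects who enter low.** Section 8.3.1 admits a neutrophil count of 1.0 × 10⁹/L, platelets of 75 × 10⁹/L, and a hemoglobin below 8.0 g/dL if corrected by growth factor or transfusion before Cycle 1 Day 1. A subject below the local range at baseline who falls to Grade 4 is counted low-to-low, which reads as no change.

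**3. Whether by-visit statistics fill the gap.** Table 5 schedules hematology on Day 15 of Cycles 1 and 2, and on Day 1 of each cycle from Cycle 2. From Cycle 3 there is no scheduled mid-cycle count. Later mid-cycle nadirs appear only in unscheduled tests, such as those done under the close monitoring of Section 8.4.1.2 or the Grade 3 retest rule. A by-visit summary does not show these, while a lowest-value table, read naturally, does. A by-visit minimum is also a single group extreme, not a count of subjects by grade.

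**4. Whether TEAEs by grade fill the gap.** Section 6.3.1 shows the effect of splitting by preferred term. Among 31 subjects in the Study 207 safety set, treatment-related Grade 3 or higher events were:
- neutropenia, 48%: 0.48 × 31 = 14.9, so 15 subjects
- neutrophil count decreased, 32%: 0.32 × 31 = 9.9, so 10 subjects
- platelet count decreased, 42%: 0.42 × 31 = 13.0, so 13 subjects
- thrombocytopenia, 29%: 0.29 × 31 = 9.0, so 9 subjects

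The overlap between paired terms is not given. The number with either neutrophil term lies between 15 (full overlap) and 15 + 10 = 25 (none), that is 48% to 25/31 = 81%. For platelets it lies between 13 and 13 + 9 = 22, that is 42% to 22/31 = 71%. These are adverse event figures, not laboratory grades. They show only that term-level tables leave the count of affected subjects open.

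**5. Precedent within the protocol.** Section 8.7.1.8.4 builds its worst-postbaseline blood pressure shift for subjects under 18 on four ordered percentile bands. An ordered severity scale for a worst-value table is already the protocol's practice elsewhere.

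**The case against.** The strongest reply is that this is detail for the SAP. Sections 8.7 and 8.7.1 defer analysis details to it, and nothing in 8.7.1.8.3 excludes a graded table. That limits the weight of the point but does not remove it, because the protocol positively chooses the scale for this table and a better one is available from the same data.

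The second reply is that severity is reported elsewhere, through by-visit values and TEAEs by highest grade. That is right, and it is why the point is minor. A reader might infer that severe cytopenia would vanish from the report, and the documents do not support that.

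A reader might also see a contradiction between Sections 8.5.1.4 and 8.7.1.8.3. There is none: a rule for grading toxicity does not fix the format of every laboratory table.

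A further tempting reading is that adverse event capture of low counts differs by arm. Section 8.5.1.4.1 says "For this study, the study drug is lenvatinib" and makes an abnormal result an adverse event if it "leads to any type of intervention, withdrawal of study drug, or withholding of study drug, whether prescribed in the protocol or not". The documents do not bear this out:
- Section 8.7.1.2 defines the safety set by any study drug, and exclusion criterion 6 lists all three drugs under that name.
- The intervention trigger applies in both arms.
- So does the adverse event reassessment at Grade 3 or higher.

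Nor does the absence of platelet and anemia rows from Table 2 show that such events go unmanaged, since Section 8.4.1.2 refers dose changes to the product information.

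**Conclusion.** The point holds as a minor, low-cost improvement. The scale fixed for the highest/lowest-value shift merges three severity bands that the protocol uses in conduct, and it hides deterioration in subjects who enter low. The other planned summaries carry much of the severity but do not give a count of subjects by worst laboratory grade under one rule for both arms.

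This rests on two assumptions: that the SAP, which is not at hand, does not already add a graded table, and that nadirs between visits are captured by unscheduled local tests. If the SAP has such a table, only the protocol wording needs aligning.

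No number of affected subjects in this trial is claimed. A reader might scale the 48% neutropenia rate of Study 207 to Arm A, but that is the adverse event rate for one preferred term and does not estimate laboratory grades. No between-arm difference is implied, and no efficacy conclusion is touched.

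**What to change.** In Section 8.7.1.8.3, for parameters that CTCAE v5.0 grades, replace the LNH shift for highest and lowest values with a shift from baseline grade to worst postbaseline CTCAE v5.0 grade, by treatment arm. State that all scheduled and unscheduled local results are used. Where CTCAE grades both directions, give one shift for each. Keep LNH for parameters that CTCAE does not grade.

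The cost is one additional derived table from results already collected. No new assessment is needed, and sample size, alpha, endpoints, decision rules and subject management do not change.
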